Appendix Table 1. Protocol Specified Contraceptive Methods

Methods to Use by Themselves	Combination Methods	
	Hormone Methods (choose one and use with a barrier method)	Barrier Methods (choose one and use with a hormone method)
Intrauterine Devices (IUDs) 
 • Copper T 380A IUD*, ** • LNG 20 IUD*** Tubal Sterilization	Estrogen and Progesterone 
 • Oral contraceptives* • Transdermal patch • Vaginal ring* Progesterone 
 • Injection • Implant* 	
 • Diaphragm with spermicide* • Cervical cap with spermicide* • Male condom (with spermicide*)
	Partner's vasectomy must be used with a hormone or barrier method and the male partner should be the sole partner for that subject. For a vasectomy, appropriate post-vasectomy documentation of the absence of sperm in the ejaculate must be available.	

Abbreviation: IUD = intrauterine device
 *Approved in Japan
 **Sold in Japan as Copper T 380 IUD
 ***Sold in Japan as Minera 52mg

The investigator will counsel all subjects on the most effective method(s) for avoiding pregnancy during the study.

4) Additional Requirements for Male Subjects

Male subjects must agree to use condoms during heterosexual intercourse and avoid sperm donation while enrolled in the study and for at least 90 days after administration of the last dose of study medication.

Use of condoms, with spermicide, has been proven to decrease the risk of transmission of HIV and other sexually transmitted diseases. The use of spermicide is not recommended if the subject or subject's partner is infected with HIV.

5) Procedures to be Followed in the Event of Pregnancy

Subjects will be instructed to notify the investigator if they become pregnant at any time during the study, or if they become pregnant within 30 days of last study drug dose. Subjects who become pregnant or who suspect that they are pregnant during the study must report the information to the investigator and discontinue study drug immediately. Subjects whose partner has become pregnant or suspects she is pregnant during the study must report the information to the investigator.

Instructions for reporting pregnancy, partner pregnancy, and pregnancy outcome are outlined in Section [7.7.2.1](#).

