3.3. Study Treatments

Approximately 200 subjects will be randomized 1:1 to receive 200 mg (four 50 mg tablets) of IMP (presatovir or placebo) as a single dose on Days 1, 5, 9, 13, and 17. The IMP will be administered orally or via NG tube. The entire dose must be taken within 1 hour. Investigational medicinal product should be dispensed with gloves.

Subjects will remain in the clinic for 30 minutes post-dose for observation. If vomiting occurs within 30 minutes after IMP administration and undissolved tablets are present in the vomitus, the subject should receive another dose. If another dose is administered, the subject should remain in the clinic for an additional 30 minutes post-dose for observation.

Presatovir will be provided as white, plain-faced, film-coated, round tablets containing 50 mg presatovir (61 mg GS-5806-02, bis-hydrochloride salt dihydrate form of presatovir). Placebo to Match will be provided as white, plain-faced, film-coated, round tablets containing no presatovir.

The expected duration of subject participation is approximately 1 month, to include Screening through the final visit on Day 28.

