6.5. Visits 6-8: Days 9, 13, and 17 (± 24 hours)

Visit 6-8 assessments must be performed in clinic or in hospital and should be performed in the following order and documented at these visits (also refer to [Appendix 2](#), Study Procedures Table):

- FLU-PRO questionnaire (Day 9 only)
- Vital Signs (body temperature, heart rate, respiratory rate, and blood pressure)
- O₂ saturation (on room air)
- Weight
- Pre-dose blood draw for central and local laboratory analysis:
 - Safety Labs (hematology and serum chemistry to include to include WBC with differential, Hgb, platelets, BUN, creatinine, serum albumin, AST, ALT, ALP, and TB)
 - Pharmacokinetic sampling for all subjects: pre-dose (Day 9 only)
 - Respiratory syncytial virus viremia
 - Local troponin testing (Day 17 only)
- Nasal samples (2 total, 1 from each nostril)
- 12-lead Pre-Dose ECG (Day 17 only)
- Urine or serum pregnancy test (for women unable to confirm menopause, hysterectomy and/or bilateral oophorectomy)
- Investigational medicinal product administration*
- Pharmacokinetic sampling for all subjects: 2 hours post-dose (± 15 min) (Day 9 only)
- Blood draw for serum creatinine at 2 hours (± 15 min) post-dose for PK subgroup subjects (Day 9 only)

- Assessment of AEs, concomitant medications, hospitalizations, re-hospitalizations, ICU admissions or utilization of ICU care > 24 hours, standard of care test results (ie, chest radiographs, microbiology, echocardiograms), mechanical ventilation (invasive and non-invasive of any duration), and supplemental O₂ use (≥ 2 L/min for >24 hours)

* Subjects will receive a single dose of 200 mg (four 50 mg tablets) of presatovir or matching placebo at Days 5, 9, 13, and 17. All IMP will be administered orally or via NG tube. The entire dose must be taken within 1 hour. Investigational medicinal product should be dispensed with gloves. Subjects will remain in the clinic for 30 minutes post-dose for observation. If vomiting occurs within 30 minutes after IMP administration and undissolved tablets are present in the vomitus, the subject should receive another dose. If another dose is administered, the subject should remain in the clinic for an additional 30 minutes post-dose for observation. Details of IMP administration are included in the Study Procedures Manual.

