6.7. Visit 10: End of Study/Day 28 (+3 days)

Visit 10 assessments must be performed in clinic or in hospital. The visit will occur no earlier than Day 28 and no later than Day 31. Visit 10 assessments should be performed in the following order and documented (also refer to [Appendix 2](#), Study Procedures Table):

- Vital Signs (body temperature, heart rate, respiratory rate, and blood pressure)
- O₂ saturation (on room air)
- Weight
- Blood draw for central and local laboratory analysis:
 - Safety Labs (hematology and serum chemistry to include to include WBC with differential, Hgb, platelets, BUN, creatinine, serum albumin, AST, ALT, ALP, and TB,)
 - Serum antibody titer to RSV
 - Respiratory syncytial virus viremia
 - Local troponin testing
- Nasal samples (2 total, 1 from each nostril)
- 12-lead ECG
- Assessment of AEs, concomitant medications, hospitalizations, re-hospitalizations, ICU admissions or utilization of ICU care > 24 hours , standard of care test results (ie, chest radiographs, microbiology, echocardiograms), mechanical ventilation (invasive and non-invasive of any duration), and supplemental O₂ use (≥ 2 L/min for > 24 hours)

6.8. Visits 11 – 14*: Days 35, 42, 49 and 56 (± 48 hours)

Visit 11 - 14 assessments may be performed in clinic, in hospital, or at the subject's home by the study coordinator or designee, or a home nursing vendor.

- Nasal samples (2 total, 1 from each nostril)
- Assessment of procedure-related AEs

PPD

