7.7.2. Instructions for Reporting Special Situations

7.7.2.1. Instructions for Reporting Pregnancies

The investigator should report pregnancies in female study subjects that are identified after initiation of study medication and throughout the study, including the post IMP follow-up period, to the Gilead DSPH using the pregnancy report form within 24 hours of becoming aware of the pregnancy.

Refer to Section [7.3](#) and the eCRF completion guidelines for full instructions on the mechanism of pregnancy reporting.

The pregnancy itself is not considered an AE nor is an induced elective abortion to terminate a pregnancy without medical reasons.

Any premature termination of pregnancy (eg, a spontaneous abortion, an induced therapeutic abortion due to complications or other medical reasons) must be reported within 24 hours as an SAE. The underlying medical reason for this procedure should be recorded as the AE term.

A spontaneous abortion is always considered to be an SAE and will be reported as described in Section [7.3](#). Furthermore, any SAE occurring as an adverse pregnancy outcome post study must be reported to Gilead DSPH.

The subject should receive appropriate monitoring and care until the conclusion of the pregnancy. The outcome should be reported to Gilead DSPH using the pregnancy outcome report form. If the end of the pregnancy occurs after the study has been completed, the outcome should be reported directly to Gilead DSPH. Gilead DSPH contact information is provided in Section [7.3](#).

Pregnancies of female partners of male study subjects exposed to Gilead or other investigational agents must also be reported and relevant information should be submitted Gilead DSPH using the pregnancy and pregnancy outcome forms within 24 hours. Monitoring of the subject should continue until the conclusion of the pregnancy. If the end of the pregnancy occurs after the study has been completed, the outcome should be reported directly to Gilead DSPH.

Refer to [Appendix 5](#) for Pregnancy Precautions, Definition for Female of Childbearing Potential, and Contraceptive Requirements.

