 - If age < 54 years and with the absence of normal menses: negative serum or urine human chorionic gonadotropin (hCG) with concurrently elevated serum FSH level in the postmenopausal range, depressed estradiol (E2) level in the postmenopausal range, and absent serum progesterone level, based on the laboratory reference ranges where the hormonal assays are performed

3) Contraceptive Requirements

Female subjects of childbearing potential and male subjects must agree to either continue abstinence from sexual intercourse or utilize protocol specified methods of contraception if they choose to engage in intercourse from the screening/enrollment visit throughout the study period

and for 30 days following the last dose of study drug (90 days for males). Female study subjects of childbearing potential will undergo regular pregnancy testing while taking presatovir. The investigator will counsel subjects on the protocol specified method(s) for avoiding pregnancy in case the subject chooses to engage in heterosexual intercourse.

Protocol specified contraceptive methods are as follows: (1) a combination of one hormonal method and one barrier method; or (2) use of an intrauterine device (IUD) or tubal sterilization; see [Appendix Table 1](#) below. Acceptable hormonal methods include injectable progesterone, progesterone implants, combination oral contraceptives, transdermal contraceptive patch, and vaginal ring. Acceptable barrier methods include diaphragm with spermicide, cervical cap with spermicide, and the male condom with spermicide. Female subjects must use either a hormonal method or a barrier method if the partner has a vasectomy and the male partner should be the sole partner for that subject. For a vasectomy, appropriate post-vasectomy documentation of the absence of sperm in the ejaculate must be available. If a subject has undergone tubal sterilization or has had a Copper T 380A IUD or LNG 20 IUD inserted, no other contraception is needed.

If tubal sterilization is via the Essure procedure, verification of tubal blockage by hysterosalpingogram (HSP) must be performed approximately 3 months after microinsertion. Prior to verification, Essure is not considered a reliable form of contraception and the contraception methods described below must be used. Female subjects who utilize hormonal contraceptives as one of their birth control methods must have used the same method for at least 3 months before study dosing.

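### Appendix 5 gives male subjects no post-dose period for reporting a partner's pregnancy, although it requires male contraception for 90 days after the last dose

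*Protocol*

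**What the plan says.** Protocol Appendix 5 sets the contraception periods in two places. Its section 3 requires contraception or abstinence from screening through the study "and for 30 days following the last dose of study drug (90 days for males"). Its section 4 requires men to use condoms and avoid sperm donation while enrolled and "for at least 90 days after administration of the last dose of study medication".

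Section 5 of the appendix then says what subjects must tell the investigator. A female subject reports a pregnancy during the study, "or if they become pregnant within 30 days of last study drug dose". For men the rule is: "Subjects whose partner has become pregnant or suspects she is pregnant during the study must report the information to the investigator".

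The next sentence of the appendix refers to Section 7.7.2.1. There, the text directed at the investigator says: "Pregnancies of female partners of male study subjects exposed to Gilead or other investigational agents must also be reported". It allows 24 hours for this, gives no closing date, and provides for outcomes that fall after study completion.

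On timing, Section 3.3 says: "The expected duration of subject participation is approximately 1 month, to include Screening through the final visit on Day 28". Section 6.7 says of the final visit: "The visit will occur no earlier than Day 28 and no later than Day 31". The last dose is given at Visit 8, and the Section 6.5 heading gives its window: "Days 9, 13, and 17 (± 24 hours").

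**The concern.** For women, the reporting instruction and the contraception period both end 30 days after the last dose. For men, contraception runs to 90 days, but the reporting sentence stops at the study itself. The protocol gives no reason for treating the two differently.

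This matters because the investigator can report only a pregnancy he or she hears about. Scheduled contact ends at Visit 10 unless the subject is in optional extended viral monitoring, so after that the man is the practical source. If he follows the sentence as written, he is not asked to report a partner pregnancy that arises in most of the period for which he must use contraception. What is at stake is the completeness of pregnancy-exposure reporting.

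**Working it through.** The plan states no figure to reproduce. The check compares the end of the male contraception period with the end of the study, in study days.

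**Inputs**
- Last scheduled dose: Day 17 (Section 3.4), window ±24 hours (Section 6.5), so Day 16 to 18.
- Male contraception: 90 days after the last dose (Appendix 5, sections 3 and 4).
- Female contraception and reporting: 30 days after the last dose (Appendix 5, sections 3 and 5).
- Final visit: Day 28 to Day 31 (Sections 3.3 and 6.7).
- Optional monitoring: last visit Day 56 ±48 hours, so Day 54 to 58 (Section 6.8). It applies only to subjects who agreed to it and test positive or inconclusive for RSV at Day 22 (Appendix 2, footnote m).

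**Formula:** uncovered days = (last-dose day + 90) − last study day.

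| Case | Calculation | Days uncovered | Share of 90 |
|---|---|---|---|
| Nominal dose, visit Day 28 | 107 − 28 | 79 | 88% |
| Nominal dose, visit Day 31 | 107 − 31 | 76 | 84% |
| Shortest over the windows | 106 − 31 | 75 | 83% |
| Longest over the windows | 108 − 28 | 80 | 89% |
| Optional monitoring counted as study, nominal | 107 − 56 | 51 | 57% |
| Optional monitoring, over the windows | 106 − 58 to 108 − 54 | 48 to 54 | 53% to 60% |
| Dosing stopped after Day 1, subject stays on study (Section 6.9.1) | 91 − 31 to 91 − 28 | 60 to 63 | 67% to 70% |

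**Female comparison:** 17 + 30 = Day 47 for both contraception and reporting, so no days are uncovered.

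**Exposure context:** Section 1.2.4.1 gives a half-life of about 36 hours after multiple doses. Five half-lives are 5 × 36 = 180 hours = 7.5 days, which puts the end at about 17 + 7.5 = Day 24.5, before the Day 28 visit. The table therefore counts calendar days without an instruction and does not measure drug exposure or risk.

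**The case against.** The strongest reply is that the operative rule is in Section 7.7.2.1, to which Appendix 5 sends the reader at once. For pregnancies in female subjects that section names a period: the study and the follow-up after dosing. For partner pregnancies it names none. A reader might infer from the appendix that the protocol stops collecting partner pregnancies at the final visit. The documents do not support that, because the investigator's duty has no end date. This part of the reply stands and confines the point to what the subject is told.

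Nor is follow-up after Day 28 merely passive. Section 7.3 does not oblige investigators to seek SAEs actively after that visit. It does require SAEs and deaths within 30 days or 4 weeks of the last dose to be reported, and also any later SAE that the investigator learns of and judges relevant to the drug. These rules cover SAEs, however, and do not tell a man to report a partner's pregnancy.

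Three further replies also carry weight:
- The appendix sentence sets a minimum; nothing forbids a later report. It could even be read so that the time limit attaches only to a suspected pregnancy, though that is the less natural reading.
- The consent form and the investigator's counselling are the usual route to the subject, and either may give a longer period.
- The 90 days looks precautionary, given the short half-life and the statement in Section 1.2.3 that genotoxic potential is considered low.

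These lower the likely consequence but do not remove the mismatch. The sponsor chose 90 days for men, and a conception late in dosing may be recognised only after the final visit. The sentence leaves it unclear whether the man must report such a case.

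**Conclusion.** The point holds in a narrow form. The subject-facing sentence in Appendix 5 has no post-dose tail for partner pregnancy, while the male contraception period in the same appendix runs 90 days and the female reporting rule matches its own period. The shortfall is 76 to 79 days nominally, 75 to 80 over the dose and visit windows, and about 51 for the subset in optional monitoring if those visits count as study.

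The figures assume that the study ends for a subject at Visit 10 and that the consent form adds nothing, which cannot be checked here. A reader might go further and conclude that pregnancies would go unreported. The documents do not show this: they do not give the number of men with partners of childbearing potential, late reports are allowed, and the investigator's duty stays open. No efficacy or safety analysis depends on the sentence. This is a minor drafting inconsistency in safety reporting.

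**What to change.** In Appendix 5, section 5, change the partner sentence to: *Subjects whose partner becomes pregnant, or suspects she is pregnant, during the study or within 90 days of the last study drug dose must report the information to the investigator.* Check that the consent form says the same.

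The cost is one sentence in an amendment, with no visit, sample or analysis added. SAP Section 1.3 records that the study was halted on 20 September 2017 at 189 subjects, so by then the main value of the change is in wording carried into later protocols.

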% AUC _{exp}	amount of Area Under the Curve that occurred after the last quantifiable sampling time point
BLQ	below the limit of quantification
BMI	body mass index
C _{last}	concentration at the last observed time point
C _{tau}	concentration for a dosing interval
C _{max}	maximum observed serum/plasma/peripheral blood mononuclear (PBMC) concentration of drug
CI	confidence interval
CL/F	apparent total clearance of drug from plasma after oral administration
CSR	clinical study report
DAVG	difference between time-weighted average post-baseline and baseline
DMC	Data Monitoring Committee
ECG	electrocardiogram
eCRF	electronic case report forms
EOT	end of treatment
FAS	Full Analysis Set
FLU-PRO	patient-reported outcome (PRO) measure to standardize the assessment of influenza (FLU) symptoms in clinical studies
HCT	hematopoietic cell transplant
HLT	high level term
HLGT	high level group term
ICH	International Conference on Harmonisation
ICU	Intensive Care Unit
ID	identification
IMP	investigational medicinal product
IWRS	Interactive Web Response System
λ _z	terminal disposition rate constant/terminal rate constant
LLOQ	lower limit of quantification
LLT	lower level term
LRTC	lower respiratory tract complication
LRTI	lower respiratory tract infection
MedDRA	medical dictionary for regulatory activities

ml	milliliter
MMRM	mixed-effect model with repeated measures
PD	pharmacodynamics
PK	pharmacokinetics
PP	Per Protocol
PT	preferred term
Q1	first quartile
Q3	third quartile
RT-qPCR	quantitative real time polymerase chain reaction
RSV	respiratory syncytial virus
SAP	statistical analysis plan
SD	standard deviation
SE	standard error
SOC	system organ class
t_{last}	time of last measurable concentration
t_{max}	time to reach maximum (peak) plasma concentration following drug administration
$t_{1/2}$	an estimate of the terminal elimination half-life of the drug in serum/plasma/PBMC, calculated by dividing the natural logarithm of 2 by the terminal elimination rate constant (λ_z)
TE	Treatment-emergent
TEAE	treatment-emergent adverse event
TFLs	tables, figures, and listings
ULOQ	Upper limit of quantification
URTI	upper respiratory tract infection
VR	ventricular rate
WHO	World Health Organization

1. INTRODUCTION

This statistical analysis plan (SAP) describes the statistical analysis methods and data presentations to be used in tables, figures, and listings (TFLs) in the clinical study report (CSR) for Study GS-US-218-0108. This SAP is based on the study protocol amendment 7 dated 28 March 2016 and the electronic case report forms (eCRF) for this study. The SAP will be finalized before the database finalization. Any changes made after the finalization of the SAP will be documented in the CSR.

1.1. Study Objectives

The co-primary objectives of this study are as follows:

To evaluate the effect of presatovir on RSV viral load and development of lower respiratory tract complication (LRTC) in RSV-positive autologous or allogeneic HCT recipients with acute upper respiratory tract infection (URTI) symptoms

The secondary objectives of this study are as follows:

- To evaluate the effect of presatovir on progression to respiratory failure or all-cause mortality
- To evaluate the pharmacokinetics (PK), safety, and tolerability of presatovir

1.2. Study Design

This is a randomized, double-blind, placebo-controlled study evaluating the effect of presatovir on efficacy, PK, safety, and tolerability in HCT recipients with RSV URTI.

All subjects will be permitted to receive the standard of care therapy for RSV infection per their local medical practices, in addition to the investigational medicinal product (IMP).

[figure not shown]
Approximately 200 subjects will be enrolled.

Subjects will be centrally randomized in a 1:1 ratio to receive IMP (presatovir or placebo) and will be stratified by 2 factors:

- Presence or absence of lymphopenia, defined as a lymphocyte count < 200 cells/ μ L versus ≥ 200 cells/ μ L of blood
- Treatment of RSV infection (yes or no) with ribavirin (oral, intravenous, or aerosolized)

A single dose of 200 mg (four 50 mg tablets) of presatovir or placebo will be administered on Study Days 1, 5, 9, 13, and 17. The study will consist of the following visits: screening (Day -1), baseline / randomization/IMP administration (Day 1), PPD Visit 3 (Day 3), Visit 4 (Day 5), Visit 5 (Day 7), Visit 6 (Day 9), Visit 7 (Day 13), Visit 8 (Day 17), Visit 9 (Day 22), and end of study (Day 28). PPD

Figure 1-1. Study Visits

1.3. Sample Size and Power

Sample size and power are estimated for the co-primary endpoints with the overall alpha level 0.05 (with alpha = 0.04 allocated to the development of a LRTC and alpha = 0.01 allocated to the time-weighted average change in viral load). The sample size calculations are based on the results observed in a study that evaluated the efficacy of oral and aerosolized ribavirin treatment for preventing progression from upper to lower respiratory tract infection in HCT recipients with RSV infections (unpublished data from [name]) and published data on currently used antiviral agents for RSV infections. {Shah 2013}

Assuming the time-weighted average change in RSV log₁₀ viral load from Day 1 to Day 9 in the placebo group will be -1 log₁₀ copies/mL, with a standard deviation (SD) of 2, 100 subjects per treatment group will provide over 80% power to detect at least 1 log₁₀ decrease in presatovir group using a 2-sided significance level of 0.01.

Assuming that 30% of subjects in placebo arm will develop a LRTC, 100 subjects per treatment group will provide over 90% power to detect at least 20% reduction in the proportion of LRTC in presatovir group with a 2-sided significance level of 0.04.

Using the fallback approach and the above assumptions for the co-primary endpoints, 100 subjects per arm will provide > 95% power to declare statistical significance in either change in viral load or proportion of subjects with LRTC.

Based on an administrative review of the data occurring in mid-September 2017, Gilead decided to halt the study on 20September2017 at an enrollment of 189 subjects despite the study not achieving complete enrollment of 200 subjects. The decision was made because enrollment of the remaining 11 subjects would have had minimal impact on study outcomes.

